Aim 2: In this cluster-randomized study, our primary outcome is change in F&V intake (cups/day) at 12 months using the 24 hour recall, thus, we will compare the difference in mean changes in F&V between intervention and comparison group participants. Our primary analysis will test the hypothesis under the intent-to-treat principle using a Generalized Linear Mixed Model (GLMM) that will account for the correlation induced by the clustering of participants within sites. The GLMM (see below) will include a random intercept for sites (β_0) fixed effects for the baseline value of the primary outcome (β_1) and the intervention (β_2) to test if the differences in mean changes in primary outcomes is zero where β_0 is the fixed intercept and e is error.

$$\text{Change in Primary Outcome}_{9m} = \beta_0 + \beta_1 \text{Primary Outcome}_{baseline} + \beta_2 \text{Intervention} + b_0 + e$$

Including the baseline values score as a covariate in an analysis of covariance (ANCOVA, in our case a GLLM ANCOVA) is known to be a more powerful test than a group comparison of baseline to post-intervention change. In order to further explore the intervention effect, we will fit FLMMs that (1) adjust for baseline covariates of interest; (2) adjust for baseline variables distributed differently between intervention groups; (3) test interaction terms between treatment group and other covariates; and (4) complete sub-group analyses. Specifically, we will look at differences in changes of F&V consumption, perceived access and self-efficacy by intervention usage. Additionally, if we see correlations between changes in F&V consumption, self-efficacy, intervention usage and/or perceived access at 12 months, we will conduct analyses to determine if these changes mediate the intervention effect. In addition, we will expand the regression models by including interaction terms to examine the heterogeneity of intervention and the role of moderators such as organizations or community types.

17.2 If applicable, provide a power analysis.

NOTE: This may not apply to certain types of studies, including chart/records reviews, survey studies, or observational studies. This question is asked to elicit whether the investigator has an adequate sample size to achieve the study objectives and justify a conclusion.

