4.3 Other Outcomes

Psychosocial measures – Self-efficacy

Self-efficacy to purchase, prepare and eat fresh F&V and will be measured with a 10-point Likert scale using a selection of items adapted from a study of shoppers where self-efficacy was shown to be correlated with nutrition behaviors and will serve as a comprehensive assessment of the effect of the educational intervention.

Psychosocial measures - Benefits (expectations)

Benefits (expectations) and barriers to eating F&V will be measured using a 4-point Likert scale (strongly agree, agree, disagree, strongly disagree) previously tested in lower-income adults which reflects common benefits/barriers found in the literature.

Psychosocial measures will be measured at baseline and 12 months.

5. Population to be Analyzed

To be eligible for the study, individuals had to be at least 18 years old, able to speak English and/or Spanish, be the primary grocery shopper for their household, and live near or otherwise regularly frequent the site. Individuals were ineligible if they were planning to leave the area or stop frequenting the site within the next year. To ensure that sites were predominantly serving lower-income community members and that the study team was sampling from the appropriate target population, a goal was set that at least 60% of eligible sign-ups are from individuals who self-report utilizing assistance programs (e.g., SNAP, WIC, TANF, Medicaid, Work First, and/or housing assistance).

6. Analyses

In order to test the impact of the VV intervention on change in F&V intake, we used generalized linear mixed model (GLMM) with random intercept to control for clustering within sites. In order to further explore the intervention effect, we fit GLMMs that adjust for (1) baseline dietary intake and (2) race and baseline income due to significant differences between groups at baseline

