(race $p=.01$; income: $p=0.02$). Including the baseline values as a covariate in an analysis of covariance (ANCOVA) is known to be a more powerful test than a group comparison of baseline to post-intervention change (42, 43). ANCOVA is not distorted by regression towards the mean bias, whereas a change analysis is subject to that bias (42, 43). We also conducted a sensitivity analysis excluding extreme F&V reporters, defined as participants who had a change (increase or decrease) greater than 10 servings of F&V per day based on generating histograms and identifying outliers in the data distribution. We conducted additional analyses comparing change in F&V intake for those who reported ever purchasing from VV (VV users) to those who did not report shopping at VV (VV non-users), including delayed-intervention control participants. Due to major disruptions to VV operations in the beginning of the study period (2020), we also looked for differences among a sub-sample of sites that launched after the peak of COVID-19 related closures defined as launching in 2021 or later (i.e., post-covid sites). All secondary outcome analyses were conducted using GLMMs and controlled for baseline covariates of interest and clustering within sites.

Additional analyses by question set can be found below:

Question Set	Answer options	Variable Creation	Analysis Plan
Demographics (13) Weight is asked again at follow-up	various	Will combine categories with small numbers of respondents BMI: created from height and weight	
For all main outcomes we need to control for site and relevant demographic variables
 
 1. Descriptive 2. Will test for differences between Ix and Control groups and include any variables that differ as co-variates in outcome analyses 3. BMI is Aim 1 outcome- compare intervention and control at 6 and 12 months. We expect BMI to stay the same for intervention at 6 months and decrease at 12 months whereas control will increase over time.

NCI F&V Screener (11)*	Frequency (per day, week or month) plus Portion Size	See below for scoring	Aim 1 Outcome. We hypothesize an increase in F&V consumption for intervention compared to control at 6 months.

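### SAP section 6 does not carry over the protocol's primary model: its lead model names only site clustering, and baseline intake appears among the exploratory models without a stated reason

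*SAP*

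**What the plan says.** Protocol 17.1 (Data Analysis, Aim 2) identifies one primary test: "Our primary analysis will test the hypothesis under the intent-to-treat principle using a Generalized Linear Mixed Model (GLMM"), with a random site intercept and "fixed effects for the baseline value of the primary outcome" as well as for the intervention. The printed equation contains the baseline term. A separate exploratory list follows: "In order to further explore the intervention effect, we will fit FLMMs that (1) adjust for baseline covariates of interest", and then models that "adjust for baseline variables distributed differently between intervention groups". Baseline F&V is not named in that list, because it is already in the primary model.

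SAP section 6 has a similar layout but different content. To test the impact of the intervention on change in F&V, "we used generalized linear mixed model (GLMM) with random intercept to control for clustering within sites". No fixed effects are listed. The exploratory sentence comes next: "In order to further explore the intervention effect, we fit GLMMs that adjust for (1) baseline dietary intake", followed by "race and baseline income due to significant differences between groups at baseline". No model is called primary. The section then states: "Including the baseline values as a covariate in an analysis of covariance (ANCOVA) is known to be a more powerful test" than comparing changes between groups, and adds that ANCOVA avoids distortion from regression to the mean.

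**The concern.** The only model that either document labels primary is the baseline-adjusted one in Protocol 17.1. In the SAP, the model used to test the intervention appears to lack the baseline term, and the baseline-adjusted model sits in the exploratory group. The SAP's own methodological remarks favour the adjusted model, so they do not explain that order.

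Timing makes this more than a matter of wording. The SAP is version 1, dated 2/3/2025. Section 6 is largely in the past tense, quotes observed baseline p-values (race .01, income 0.02) and sets its extreme-reporter cut-off from histograms of the data. When the data are already in hand, the confirmatory test should be identifiable without inference. At stake are some precision and the existence of two estimates that could each be presented as the main result.

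**Working it through.** **1. The two texts side by side.**

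| | Protocol 17.1 | SAP section 6 |
|---|---|---|
| Labelled primary | Yes | No model labelled |
| Lead model, terms named | Baseline F&V, intervention, site intercept | Site intercept only |
| Exploratory item 1 | Baseline covariates of interest | Baseline dietary intake |
| Exploratory item 2 | Baseline variables that differ between groups | Race and baseline income, because they differed |

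Item 2 matches across the documents, so the baseline term is the apparent difference. The SAP does not define baseline dietary intake. Its next sentence speaks of including the baseline values as a covariate, which points to baseline F&V.

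**2. Reproducing the plan's power.** Inputs from SAP 2.1: SD of change 2.7, ICC 0.08, 21 per site, 12 sites per arm, difference 1.0 cup/day, one-sided 0.05.

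- Site variance: 0.08 × 2.7² = 0.583. Person variance: 0.92 × 2.7² = 6.707; divided by 21, 0.319.
- SE = √[2(0.583 + 0.319)/12] = 0.388.
- Noncentral t with 2(12 − 1) = 22 df: power 0.803. This matches the 0.80 in SAP Table 1, so the plan was powered on the unadjusted change score.
- Site share of the squared SE: 0.583/0.902 = 65%.

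**3. Effect of adding baseline F&V.** Assumptions not in the documents: equal variances at both times and a baseline-to-12-month correlation r of 0.3 to 0.6. Change has variance 2σ²(1 − r) and the ANCOVA residual has σ²(1 − r²), so the ratio is f = (1 + r)/2 = 0.65, 0.75, 0.80 for r = 0.3, 0.5, 0.6. Because site variance dominates, two cases are shown for k sites per arm:

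- ICC held: SE = √[2f(0.583 + 0.319)/k].
- Site variance unchanged: SE = √[2(0.583 + f × 0.319)/k].

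| k = 12, 21 per site | SE | SE cut | Power |
|---|---|---|---|
| Change score | 0.388 | – | 0.803 |
| Adjusted, site variance unchanged (r = 0.3 / 0.5 / 0.6) | 0.363 / 0.370 / 0.374 | 6.4 / 4.5 / 3.6% | 0.847 / 0.834 / 0.828 |
| Adjusted, ICC held (r = 0.3 / 0.5 / 0.6) | 0.313 / 0.336 / 0.347 | 19.4 / 13.4 / 10.6% | 0.927 / 0.892 / 0.874 |

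With 16 sites per arm (the SAP's 32 sites) and 21 per site, power is 0.897 for the change score, 0.915–0.928 adjusted with site variance unchanged, and 0.946–0.975 with the ICC held.

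**4. When the gain disappears.** Let t be the site variance at each time and c the site-level correlation over time. Applying the person-level slope r to site means turns the site variance from 2t(1 − c) into t(1 + r² − 2rc). The site-variance-unchanged case corresponds to c = (1 + r)/2. The total gain reaches zero at c = 0.725, 0.804 and 0.843 for r = 0.3, 0.5 and 0.6.

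**5. Two candidate tests.** In a null simulation with equal site variances at both times (12 and 16 sites per arm, 21 per site, r as above), each test alone held about 5% one-sided error. Declaring success when either was significant gave about 7–8%.

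**6. Participants lost by adjusting.** None. Protocol 10.1 says Phase 2 participants have no baseline recalls, but the change score needs those recalls too.

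**The case against.** The strongest reply is that the SAP's lead sentence describes a class of model and is not a full specification. It does not even state the intervention term, so its silence on baseline is weak evidence of omission. Nor is baseline dietary intake necessarily baseline F&V. Protocol 10.2 derives calories, percent of calories from F&V and added sugars from the same recalls, and a broader variable would fit the protocol's exploratory item 1, in which case nothing moved. This stands as a limit on certainty. It does not remove the problem: if the lead sentence is shorthand, the SAP still leaves its primary test unstated.

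It is also true that the adjusted model is reported as fitted, that Protocol 17.1 still names the primary model, and that the precision argument rests on correlations the documents do not give.

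A reader might infer three stronger things, and the documents support none of them. The first is that the order was changed after outcome results were seen, or that the team would report whichever model was significant; nothing shows when or why the order arose. The second, prompted by the SAP's remark on regression to the mean, is that the change-score test is biased; under randomisation it is unbiased on average. The third is that the trial loses its planned power; the change-score model is the one that reproduces 0.80.

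**Conclusion.** The discrepancy holds, with medium confidence in the reading. Protocol 17.1 has a named, baseline-adjusted primary test. SAP section 6 has no named primary test, and its lead model is most likely the unadjusted change-score model. The departure is unexplained and runs against the SAP's own argument.

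The cost is moderate. Given r of 0.3 to 0.6 and equal variances, the SE is about 4–6% larger than it need be relative to the unadjusted value if site variance is unchanged by adjustment, or 11–19% if the ICC is held. Power at 12 × 21 per arm would rise from 0.80 to 0.83–0.85 or 0.87–0.93. The gain is not guaranteed and can vanish if site means are strongly correlated over time. The roughly 7–8% one-sided error describes what would happen if either model could be chosen; it is not a statement that this was done. The reason to act is mainly the unexplained departure from the named primary test, which depends on none of these assumptions.

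**What to change.** In SAP section 6:

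- Name one primary test: the mixed model for 12-month change in F&V with baseline F&V (cups/day from the two baseline recalls) and intervention as fixed effects and a random site intercept.
- Define baseline dietary intake, and say whether it is that same variable.
- Label the model without baseline F&V, and the model adding race and income, as sensitivity analyses.
- If the departure from Protocol 17.1 was intended, give the reason and the date of the decision.

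Two points in Protocol 17.1 should not be copied across. The outcome in the equation is subscripted 9m although the text says 12 months; correct it to 12 months. The text, as it reads here, gives β_0 for both the random site intercept and the fixed intercept, while the equation prints a separate b_0; use separate symbols throughout.

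The cost is a few sentences. A model adjusting for baseline dietary intake is already reported as fitted; if that variable is not baseline F&V, one refit is needed. No further data are required.

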[figure not shown]
Statistical Analysis Plan (SAP)

Effectiveness and Implementation of a Research Tested Mobile Produce Market Designed to Improve Diet in Underserved Communities

Principal Investigator	[name] Associate [name] of Community Health and Health Behavior School of Public Health University at Buffalo Buffalo, NY
Protocol identification number	1144594
ClinicalTrials.gov identifier	NCT04246593
Author	[name], PhD Assistant Director of Research and Evaluation Community Health Interventions Lab Department of Community Health and Health Behavior School of Public Health University at Buffalo Buffalo, NY
Version	1
Date	2/3/2025

SIGNATURE PAGE

Principal Investigator

[name]

Author

[name]

ABBREVIATIONS

BMI	Body Mass Index
F&V	Fruits and Vegetables
MM	Mobile Market
RFP	Request for Partners
SAP	Statistical Analysis Plan
SNAP	Supplemental Nutrition Assistance Program
TANF	Temporary Assistance for Needy Families
VV	Veggie Van
WIC	Special Supplemental Nutrition Program for Women, Infants, and Children

TABLE OF CONTENTS

1. Introduction.....	5
2. Study design.....	5
2.1 Sample size calculation.....	7
3. Aims and objectives	8
4. Outcomes	8
4.1 Primary Outcome	8
4.2 Secondary Outcomes.....	9
4.3 Other Outcomes.....	9
5. Population to be Analyzed	9
6. Analyses.....	9

1. Introduction

The goal of the Veggie Van (VV) study is to evaluate the effectiveness of mobile produce markets using the VV mobile market (MM) model through a 12-month cluster-randomized controlled trial in 33 communities.

This statistical analysis plan (SAP) will describe the endpoints of the study and the analyses to evaluate our main outcomes.

2. Study design

We utilized a request-for-partners (RFP) process to recruit organizations as study partners; nine organizations were selected as partners and asked to implement the Veggie Van model at new mobile market sites and facilitate recruitment of mobile market customers for the study and data collection activities. Each study partner organization was asked to partner with four community sites that serve as potential locations for the mobile market program, known as community sites.

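### SAP version 1 was finalised after data had been inspected and does not say so; it adds two analyses and moves baseline adjustment out of the main model, so readers cannot tell which result was fixed in advance

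*SAP*

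**What the plan says.** The SAP introduction presents a plan: "This statistical analysis plan (SAP) will describe the endpoints of the study and the analyses to evaluate our main outcomes". Section 6 (Analyses) mostly reports work already done:

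- **Main question.** It states that "we used generalized linear mixed model (GLMM) with random intercept to control for clustering within sites". The fixed effects of this model are not listed.
- **Further exploration.** Models adjusting for baseline dietary intake come next, followed by adjustment for "race and baseline income due to significant differences between groups at baseline". The observed p-values are printed: 0.01 for race and 0.02 for income.
- **Sensitivity analysis.** This drops participants with "a change (increase or decrease) greater than 10 servings of F&V per day". The limit was set "based on generating histograms and identifying outliers in the data distribution".
- **Site subset.** One analysis is restricted to sites launched in 2021 or later, because operations were disrupted in 2020.

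The SAP gives no data-lock date and no date of first look at the data by arm. It does not mark which choices came before the data and which after.

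Protocol 17.1 is forward-looking: "Our primary analysis will test the hypothesis under the intent-to-treat principle". Its model is a GLMM with a random site intercept and fixed effects for the baseline value and the intervention. In general terms it also plans adjustment for baseline variables that differ between arms, interaction tests, unnamed subgroup analyses and comparisons by use of the market.

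**The concern.** A document titled as a statistical analysis plan is normally taken to record what was fixed before results were known. This one contains choices that could only have been made with data in view, and it does not separate them from the rest. The protocol and SAP also disagree on whether the main test adjusts for baseline intake, and the SAP is the later, data-informed source. A reader who finds the two models, the exclusion and the subset giving different answers cannot tell from the documents which one is confirmatory. Only a test fixed in advance keeps its nominal error rate.

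**Working it through.** The plan states no error rate for these analyses, so there is no figure to reproduce. The check compares the two documents and then illustrates the size.

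**1. What must have been seen before SAP 6 was finalised**
- Allocation with baseline data: covariates are named "due to significant differences between groups at baseline", with p-values.
- 12-month primary-outcome data: a limit on change cannot be read from histograms without follow-up recalls. The text does not say that the histograms were split by arm.
- Outcome models by arm: inferred from the past tense only. No outcome result by arm is printed.

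**2. Protocol 17.1 against SAP 6**

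| Analysis | Protocol 17.1 | SAP 6 |
|---|---|---|
| Baseline intake as covariate | In the primary model | Listed as further exploration |
| Exclusion of changes above 10 servings/day | Absent | Sensitivity analysis, limit read from the data |
| Sites launched in 2021 or later | Not named; subgroups planned generically | Named subset |
| Race and income adjustment | Planned by rule, variables not named | Rule applied to observed differences |
| Users against non-users | Planned generically by usage | Definition given |

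The first three rows carry the point; the last two carry out something 17.1 announced. The first row rests on a reading: SAP 6 does not list the main model's fixed effects, but a separate later model for baseline intake implies that the main model lacks it. SAP 6 then argues that ANCOVA is more powerful and avoids regression-to-the-mean bias, which supports the protocol's choice of primary model.

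**3. Illustration of size, with no true effect**

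Document inputs are ICC 0.08, SD of change 2.7 cups/day, and 21 participants per site at 32 sites. The rest is assumed.

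- *Simulation A:* 2,500 trials, paired sites, heavy-tailed residuals, two-thirds of sites launching in 2021 or later, limit equal to 5 cups, random-intercept fits with sites − 2 degrees of freedom, nominal 5%. One test rejected in 4.8% of trials. At least one of the three adjustment models rejected in 6.6%. At least one of 12 (3 adjustments × 2 exclusion rules × 2 site sets) rejected in 13.0%.
- *Simulation B:* 4,000 trials per setting, one-sided 0.05, 16 sites per arm, t tests on site means, correlation −0.5 between baseline and change. The five analyses were unadjusted, baseline-adjusted, exclusion, site subset, and site subset with baseline adjustment. Each alone rejected in 4.4–5.6%. At least one rejected as follows:

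| Limit | 50% of sites 2021 or later | 75% of sites 2021 or later |
|---|---|---|
| 5 cups | 10.8% | 10.0% |
| 10 cups | 10.2% | 8.7% |

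Five independent tests would give 1 − 0.95^5 = 22.6%. The simulated rates are lower because the analyses share data.

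**4. Why the serving-to-cup conversion matters**

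The limit is in servings and the outcome is in cups, with no conversion given. If change is normal with mean 0 and SD 2.7, a 5-cup limit sits at 5/2.7 = 1.85 SD and removes about 6.4% of participants. A 10-cup limit sits at 10/2.7 = 3.70 SD and removes about 0.02%.

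**The case against.** Several points on the other side stand.

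- SAP 6 ranks its analyses (a main test, further models, a sensitivity analysis, additional analyses) and discloses how the limit was set. It never calls the added analyses prespecified. Those labels give an analysis's role, however, and not when it was chosen.
- The race-and-income model follows a rule in protocol 17.1, repeated in the future tense in the SAP's question-set table. Such a rule cannot name variables before baseline data exist. A reader might infer that this adjustment is absent from the protocol; it is not.
- The 2021-or-later subset has an external reason and is defined by launch date. Nothing shows that outcome data prompted it.
- The SAP is a composite. Sections 2 to 4 and the question-set table are largely forward-looking, so it does not follow that the whole document was conceived after the data.

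Two stronger readings are tempting. One is that analyses were selected after their treatment effects were seen. The documents do not establish this: the only arm comparisons printed are of baseline variables, and the histograms need not have used allocation. The other is that the trial's false-positive rate is 13%. That figure crosses options into 12 models, which the SAP never does. It also counts the protocol's own primary model and the rule-based adjustment, and it applies only if any favourable variant could support the conclusion, a rule the SAP does not state.

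**Conclusion.** The point holds in limited form. SAP version 1 postdates inspection of baseline differences by arm and of the distribution of 12-month change, and it does not say so. It adds one data-driven exclusion and one subset not named in advance. By implication it also moves baseline adjustment out of the main test. The last matters most, because it leaves two candidates for the confirmatory result.

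If any variant could carry the conclusion, the null rejection rate rises from about 5% to roughly 7–13%. The value depends on how many variants are counted, the share of sites launching in 2021 or later, the serving-to-cup conversion and sidedness. The documents fix none of these for these analyses; the one-sided 0.05 appears only in the sample-size calculation. The range illustrates why labelling matters and is not an estimate of this trial's error rate. The protocol's primary analysis is intact and can still be reported as planned.

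**What to change.** In SAP 6:

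1. State that version 1 was finalised after the data had been inspected, and give the dates of data lock and of first look by arm.
2. Name the protocol 17.1 intent-to-treat GLMM, with the baseline value as covariate, as the single confirmatory test. Write it for the 12-month change given in the protocol text, since the displayed equation carries a nine-month subscript.
3. Report the model without baseline adjustment as supportive.
4. Label the exclusion of changes above 10 servings/day (data-driven) and the 2021-or-later subset (not named in advance) as post hoc and exploratory, in the SAP and in the results tables. Neither should be the basis for the effectiveness conclusion.
5. Describe the race-and-income model as planned by rule in 17.1, with its variables chosen from observed baseline differences.

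The cost is wording and table labels; no new data are needed. The downside for the investigators is that a favourable post hoc result can no longer be presented as planned.
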